**Table: Examples of indirect measures of economic consequences**

1. Borrowing or selling household assets as a result of injury
2. Loss of household income as a result of the injury
3. Lost work by any member of the household as a result of the injury
4. Missed school by any member of the household as a result of the injury
5. Household food insecurity as a result of the injury
6. Any member of the household serving as a caregiver for the injured person.

level at 4 weeks, 3 months and 6 months after injury. Triage-tool contact will be evaluated for prediction of economic disability and presentation for follow-up care (both considered as binary variables) using univariate and adjusted multiple logistic regression.

**Outcomes:** Primary outcomes will include proportion of injured patients who seek clinical follow-up evaluation. Secondary outcomes will include GOSE disability level, work lost and other economic consequences of injury, such as spending savings and borrowing money.

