## 2. STUDY AIMS

The primary study objectives are as follows:

**Aim 1: Establish the feasibility of using mobile phones to follow up on hospitalized trauma patients after discharge in Cameroon.**

*Hypothesis:* Mobile phones are a feasible way of contacting trauma patients after they are discharged from the hospital in Cameroon.

We will contact trauma patients discharged from four hospitals participating in the Cameroon National Trauma Registry at intervals of two weeks, one month, three months, and six months following discharge. The response rate and decay of response over time will be tracked.

**Aim 2: Cross-validate a telephone-based triage tool to identify trauma patients who would benefit from further medical care.**

*Hypothesis:* A triage tool administered over the telephone can effectively identify injured patients who would benefit from further care for their injuries.

An over-the-phone triage tool will be used to predict a binary outcome two-weeks after discharge: needs further care or does not need further care. An independent physician blinded to triage tool outcome who will also render a determination on the same binary outcome, will examine those patients contacted by telephone. Physician assessment will be used as the gold standard to calibrate the model, which will be validated in a separate patient cohort.

**Aim 3: Characterize the impact of timely follow-up on long-term disability and socioeconomic consequences associated with trauma in Cameroon.**

*Hypothesis:* Trauma patients in need of post-hospitalization medical care will have improved disability outcomes if follow-up care is delivered promptly.

Patients will be given a modified Glasgow Outcomes Scale-Extended (GOSE) survey to complete at two weeks, one month, three months, and six months after hospitalization to quantify the death and disability associated with traumatic injury for each patient. Pre- and post-intervention results will be compared.

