**Implementation/Data Collection:** Injured patients who are successfully contacted at any of the study time points following hospital discharge will answer an over-the-phone survey to assess disability using an augmented GOSE (aGOSE) instrument, which is a metric of multi-domain functional status initially targeted for patients following neurologic trauma. It has since been validated in diverse geographic locations and in broader clinical contexts. Additional questions to evaluate economic consequences of injury will be added to the existing GOSE instrument. As our preliminary experience indicates that respondents are extremely reticent to speak directly about money over the phone, indirect measures of economic consequences will be emphasized (**Table**). Respondents will also be asked whether they sought further care for their injuries and if so, whether care was rendered. Six months before we begin using the telephone triage tool we will collect baseline data at all 4 facilities, after which the triage tool will be implemented in a stepped-wedge fashion in the 4 facilities, staggered by three months for each facility's start date. The cohort of patients (or their surrogates) who answer the triage survey will also be asked to answer the aGOSE, which will be administered at 2-weeks and at 1, 3, and 6 months. This design will let us compare intervention patients with historical controls, while controlling for temporal trends.

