**Data Analysis:**

As this study is powered for cross-validation of the triage tool, aim 3 is exploratory in nature and may not detect a difference in validated disability metrics between the intervention control cohorts. Therefore, process improvement indicators will serve as the primary outcome measures for this aim, and disability and economic outcomes will be secondary outcomes. These results will let us calculate effect size for future prospective validation of the triage tool. Summary measures of all outcomes will be calculated using medians and interquartile ranges for numeric and ordinal variables and proportions for binary and categorical variables. Outcome metrics will be stratified by hospital site, injury severity, age, and economic indicators at each time point. Trends in physical and economic disability will be assessed over time. Process outcomes, disability measures, and disability distributions will be compared between baseline and intervention cohorts using Kruskal-Wallis one-way analysis of variance for numerical and ordinal variables and chi-square tests for categorical variables. Univariate linear regression and multiple regression adjusting for age, gender, mechanism, injury severity, and hospital site will be used to assess triage-tool contact as a predictor of GOSE disability

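### Aim 3 measures aGOSE on the same patients four times but names no repeated-measures or trend method; one likelihood-based longitudinal model would use the data better, with a modest and conditional gain

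*Combined protocol and SAP*

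**What the plan says.** The Aim 3 Implementation/Data Collection paragraph describes one cohort followed with the aGOSE, "which will be administered at 2-weeks and at 1, 3, and 6 months". Data come from whoever is reached: "Injured patients who are successfully contacted at any of the study time points following hospital discharge will answer an over-the-phone survey".

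The Aim 3 Data Analysis paragraph, which continues after the table of economic measures, names these methods:

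- Summaries by call: "Outcome metrics will be stratified by hospital site, injury severity, age, and economic indicators at each time point".
- Cohort comparisons with independent-sample tests: outcomes are "compared between baseline and intervention cohorts using Kruskal-Wallis one-way analysis of variance for numerical and ordinal variables", with chi-square tests for categorical variables.
- Regression: "Univariate linear regression and multiple regression adjusting for age, gender, mechanism, injury severity, and hospital site will be used to assess triage-tool contact". The outcome in these models is the GOSE, taken at three times: "level at 4 weeks, 3 months and 6 months after injury".
- Trends: "Trends in physical and economic disability will be assessed over time", with no method given.

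Nowhere does the plan name a patient effect, a within-patient correlation, a cohort-by-time term or a missing-data method. The 2-week aGOSE is collected but is not among the regression time points. Under Aim 1, section 2 does anticipate falling response ("The response rate and decay of response over time will be tracked"), but this is not carried into Aim 3. The plan declares Aim 3 exploratory and ranks GOSE as a secondary outcome.

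**The concern.** The natural reading is a separate regression at each of three times. Each regression then ignores what the same patient reported at other calls, and a patient who misses a call adds nothing at that time. If the people who answer at 6 months differ from those who answered at 1 month, a curve drawn from per-call summaries shows recovery and changing response together. If response also differs between the baseline and intervention cohorts in a way related to outcome, the cohort comparison at a given call is biased too.

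If the three times were instead meant to be pooled in one ordinary regression, ignoring within-patient correlation would make the standard errors wrong. Either way the wording needs completing.

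What is at stake is the quality of the effect size that Aim 3 is meant to supply for a later study, and the reading of the recovery curves. No confirmatory conclusion depends on it.

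**Working it through.** **The plan's own figure.** No power, SD, correlation or precision is given for Aim 3. The stated size reproduces as 13 variables × 10 per variable ÷ 0.10 = 1300, but it belongs to Aim 2. Everything below therefore rests on stated assumptions.

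**Inputs from the plan.** In the pilot (telephone triage tool paragraph), 64% of numbers were reached and 39% of subjects or families took part in surveys; contact was 68% at 3 months and 61% at 6 months, in separate groups of patients. The plan says that longitudinal response is not known and expects it to rise.

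**Assumed inputs.** Within-patient correlation ρ; response at 2 weeks and 1 month; the pattern of missed calls.

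**1. Precision at one time point (6 months).** If all earlier calls are answered and a fraction p answers at 6 months, then

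variance(joint) ÷ variance(per-call) = 1 − (1 − p)R²,

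where R² is the share of 6-month variance explained by the earlier calls.

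- Complete data, p = 1: ratio 1, so no gain at any ρ.
- p = 0.61, ρ = 0.5, equal correlations: R² = 3ρ²/(1 + 2ρ) = 0.75/2 = 0.375. Ratio = 1 − 0.39 × 0.375 = 0.854, and the SE falls by 7.6%.
- p = 0.61, ρ = 0.5, correlation decaying with time (AR(1)): R² = ρ² = 0.25. Ratio = 1 − 0.39 × 0.25 = 0.9025, and the SE falls by 5.0%.

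Earlier calls will be incomplete too, which lowers these figures. Generalised least squares with separate call means, equal or AR(1) correlation, and monotone or intermittent missingness gives:

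| Response at 2 weeks, 1, 3, 6 months | Fall in 6-month SE, ρ = 0.5 | Range, ρ = 0.3 to 0.85 |
|---|---|---|
| 100/100/100/100% | 0% | 0% |
| 100/90/80/70% | 1.9% to 5.6% | 0.6% to 12.7% |
| 100/85/68/61% (last two are pilot contact rates) | 2.0% to 7.2% | 0.5% to 16.9% |
| 100/80/60/39% | 5.1% to 11.2% | 1.7% to 27.9% |

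**2. Precision of an average over the three later calls.** With equal correlation, k answers carry k/(1 + (k − 1)ρ) times the information of one.

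- Same patients always answer, ρ = 0.6: 3/2.2 = 1.36. SE ratio = 1/√1.36 = 0.86, a 14% reduction. This holds at any response rate. At ρ = 0.4 the ratio is 3/1.8 = 1.67; at ρ = 0.8 it is 3/2.6 = 1.15.
- Answering independent between calls at 39%, ρ = 0.6: the chances of 1, 2 and 3 answers are 0.435, 0.278 and 0.059. Information = 0.435 × 1 + 0.278 × 1.25 + 0.059 × 1.364 = 0.864, and 0.864/0.39 = 2.22. SE ratio 0.67, a 33% reduction. The share with at least one later answer is 1 − 0.61³ = 77%.

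**3. Bias.** A simulation with 100,000 patients per cohort, a true cohort difference of 0, about 60% response at 6 months and ρ = 0.3/0.5/0.7 gave these errors at 6 months, in SD units:

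| Non-response | Quantity | Per-call | Joint likelihood model |
|---|---|---|---|
| Missing at random, opposite direction in the two cohorts | cohort difference | 0.16/0.27/0.38 | about 0 |
| Missing at random, same in both cohorts | cohort difference | about 0 | about 0 |
| Missing at random, same in both cohorts | mean level | −0.08/−0.13/−0.19 | about 0 |
| Missing not at random, opposite direction | cohort difference | 0.31/0.35/0.42 | 0.24/0.19/0.13 |

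**The case against.** A reader might infer that a joint model is simply more precise and less biased than what is planned. The documents do not support that.

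- **Wording.** The plan never says that the regressions are separate or that trends come from per-call summaries. This stands: the supportable complaint is an incomplete method, not a demonstrably wrong one.
- **Different estimands.** The 14% figure compares an average over three calls with one call, whereas the plan names three time-specific effects. This stands. For those effects the gain is zero with complete data and small at pilot-like contact rates.
- **Independent answering is implausible.** The 33% and 77% figures need it. The pilot's main failures were respondents who did not know the patient (37%) and disconnected phones (29%), which probably persist from call to call, and the Informed Consent section ends contact with households that decline at two weeks. The 39% also comes from a retrospective pilot that used an unrecognisable number. This stands, and those figures should not be relied on.
- **Bias is not always reduced.** When non-response worked alike in both cohorts, the cohort difference was about unbiased under either approach. Patients never reached add no GOSE to either model. This stands, but the mean levels, and so the recovery curves, were still wrong in the per-call analysis.
- **Importance.** Aim 3 is exploratory, GOSE is secondary, and the Addendum describes data collection as finished. This limits the weight of the point. It does not remove the need to name a method for trends and for repeated, incomplete measurements.

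**Conclusion.** The point holds in a limited form. For an outcome measured four times on the same patients, with non-response expected, the plan names only single-time methods and leaves the trend analysis unspecified.

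The precision gain is conditional: none at a given call with complete data, and about 2% to 7% in the 6-month SE at pilot-like contact rates with ρ = 0.5. An average over the later calls would be about 14% more precise than one call at ρ = 0.6 with the same responders, as an additional summary rather than a better estimate of the same quantity. All correlations and response patterns here are assumptions.

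The bias gain depends on observed GOSE explaining non-response. Where it does not, bias was reduced but not removed in the case simulated.

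It would also be wrong to infer that a longitudinal model restores a controlled comparison. The Addendum records that the stepped wedge was abandoned, and confounding of the before-after contrast by time remains whichever model is used. The change is worth making, but its impact is modest.

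**What to change.** Specify one likelihood-based longitudinal model for aGOSE:

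- Use all answers, including the 2-week call, kept as an observed response because it is the earliest information on who later drops out.
- Include a patient random effect and terms for cohort, call time, cohort-by-time, age, gender, mechanism, injury severity and hospital site.
- Prefer an ordinal model with death as its own level. Section 2 makes death part of what the GOSE is to quantify, so it should not be treated as a missed call.
- Do not substitute unweighted GEE, which generally needs data missing completely at random.
- Report the time-specific cohort effects and, as a summary, the average effect over the three later calls. Use the interaction to show whether an average is a fair summary.
- Draw recovery trends from the model, and add a sensitivity analysis for data missing not at random.
- State one time origin: the regression counts from injury, whereas the calls are scheduled from discharge.

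No new data are needed. The cost is plan wording and slightly more analysis. If the model is adopted after data collection, it should be labelled post hoc.

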4	Do they need daily help from another person to feed, clothe, bathe, and go to the toilet?	 Yes  No
5	Since leaving the hospital have they had problems...	 Getting food or water?  Taking medicines?  Caring for your injury/wound as instructed?
6	Since leaving the hospital have any of the following things STARTED or GOTTERN WORSE?	 Fever  Redness/Swelling of the injured part  Pain  Difficulty moving or feeling  Drainage or opening of a wound/incision
7	Since leaving the hospital, have they seen another doctor or healer for the injury?	 No  Considered seeking additional treatment  Sought other care but no further treatment given  Received additional treatment

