## APPROACH

**Aim 1: Establish the feasibility of using mobile phones to follow up on hospitalized trauma patients after discharge in Cameroon.** This aim will be addressed through a prospective cohort study following discharged trauma patients longitudinally over 6 months. The following data will be extracted from the existing trauma registry: patient demographics, clinical course, injury severity, disposition, and patient cell phone numbers. All admitted trauma patients who provided cell phone numbers in the emergency department will be contacted at intervals of 2 weeks and 1, 3, and 6 months post-discharge. Contact points at 2 weeks and 1 month correspond with traditional post-injury follow-up visits when intervention is theoretically likely to positively impact patient trajectory. These time points have also been used in prior mobile-health follow-up studies in traumatic brain injury and surgical patients in developed settings. Three and 6-month time points were selected because our preliminary data showed higher rates of disability and survey response at 3 and 6 months than at 12 months. Attempts will be made to contact patients at least 3 times by calling and once by text message over a 1-week interval at each time point.

**Outcomes:** number and proportion of successful attempts.

[figure not shown]
**Sample Size:** This overall study is powered for Aim 2 (see below), but the study population for Aim 2 will be used to calculate the number and proportion of successful attempts in Aim 1.

**Data Analysis:** Feasibility will be assessed through calculation of the number of successful contacts; number of attempts required to achieve success; cost associated with personnel and telephone time; reason for contact failure; and survey administration time. Frequencies and proportions of successful contacts will be calculated for each time interval and temporal trends will be described. Mean and standard deviation for personnel time and call cost will be used to calculate average cost per patient contact and determine the overall feasibility of cell phone interviewing as a follow-up method.

**Aim 2: Cross-validate a telephone-based triage tool to identify trauma patients who would benefit from further medical care.**

**Study design:** The 4 hospitals will start in a stepped wedge design the implementation of mHealth telephone triage tool (see Figure 1).

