**Implementation/Data Collection:** Patients contacted two weeks after discharge will be asked to give additional consent for participating in the triage tool part of the study. Those who consent will be contacted by research assistants and will answer 7-question survey. Patients whose responses trigger concern about the need for further medical attention will be informed that they should return to care and given appropriate instructions. All patients, regardless of triaged status, will be asked to schedule a time for a physical exam and will undergo one either at the hospital or in their place of residence. If patients return to the hospital, compensation for travel expenses will be provided on a sliding scale. This exam will occur within 1 week of the phone interview. Trained study physicians will conduct a structured, standardized exam that will ultimately culminate in a dichotomous outcome for “needs further care” or “does not need further care”. Based on the exam, the physician will determine if the patient would benefit from further services (including additional follow-up care, diagnostic or therapeutic interventions). Additional data will be collected regarding physician opinion as to whether the patient is demonstrating on-trajectory recovery for their age, health status, and injury, and whether the patient is at high, moderate, or low risk for a poor outcome. At the 2-week and 6-month time points, all contacted patients will be asked about their satisfaction with formal medical services, post-injury follow-up care, perceived convenience, and utility of mobile telephone follow-up.

**Figure 1: Step-wedge design of study.** For each site: Diagonal lines depict a GOSE baseline data collection phase, gray arrows depict intervention phase (1 year/site), and black blocks depict follow-up phase (6 months/site).

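### Aim 3 labels as a triage-tool effect what is the effect of the triage call plus a study physician exam, and does not say that the exam visit is left out of the care-seeking outcome

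*Combined protocol and SAP*

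**What the plan says.** **Exposure and outcome.** Section 3A, Aim 3, Data Analysis compares process outcomes and disability between the baseline and intervention cohorts. It then uses triage-tool contact as the predictor of GOSE level, economic disability and presentation for follow-up care. The same section says the results will be used to calculate an effect size for future prospective validation of the tool. The Outcomes paragraph states: "Primary outcomes will include proportion of injured patients who seek clinical follow-up evaluation". No further definition is given.

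**What intervention patients receive.** Under Aim 2, Implementation/Data Collection, patients whose answers raise concern are "informed that they should return to care and given appropriate instructions". The exam is not limited to them: "All patients, regardless of triaged status, will be asked to schedule a time for a physical exam and will undergo one". The visit may take place at home instead of at the hospital. On timing, "This exam will occur within 1 week of the phone interview". On cost, "If patients return to the hospital, compensation for travel expenses will be provided on a sliding scale".

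**What baseline patients receive.** Aim 3, Implementation/Data Collection and the Addendum describe baseline as collection of aGOSE data. No exam is mentioned for that phase.

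**How care-seeking is measured.** Aim 3, Implementation/Data Collection: "Respondents will also be asked whether they sought further care for their injuries and if so, whether care was rendered". Section 10 adds verification against medical records where possible. Neither place mentions the study exam.

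**The concern.** There are two separate issues.

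1. **Attribution.** The phases differ by a phone triage and by a physician exam that ends in a decision on whether further services would help. The analysis names only the first. An effect size labelled as that of the tool would be carried into the planning of a later study, where the tool might be used without a universal exam.

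2. **Outcome definition.** If a study-arranged exam visit is recorded as follow-up that the patient sought, the intervention proportion rises with no change in patient behaviour. Baseline patients have no corresponding visit.

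The exam is the reference standard for Aim 2, so doing it is not in question. What is at stake is what Aim 3 can claim.

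**Working it through.** No figure in the plan bears on this point, so there is none to reproduce. The check is mainly a comparison of sections.

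**Step 1. Is the exam confined to one phase?** Aim 2 asks all triage participants to have it, whatever their triage result. The baseline descriptions contain only the survey. The exam is therefore a systematic difference between phases.

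**Step 2. Can tool and exam be separated?** The Addendum says they were designed to be rolled out together, that the tool was held back when exams could not be done, and that the tool was given with physician exams from February 2020 to August 2022. It also dates the first exams to one month before a suspension placed in April 2020, which could suggest a slightly later start than February. Even so, no tool-only period is described. The adjustment variables in Aim 3, Data Analysis (age, gender, mechanism, injury severity, site) do not separate the two.

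**Step 3. Which time points are affected?** The exam falls at 2 weeks + up to 1 week = up to 3 weeks after discharge. If the call succeeds only at the end of the one-week contact window, taken to open at 2 weeks, this becomes up to 2 + 1 + 1 = 4 weeks. The 2-week survey mostly precedes the exam, and the 1-, 3- and 6-month surveys follow it. The GOSE regression is set at 4 weeks, 3 months and 6 months. The plan counts these from injury; they are read here as the 1-, 3- and 6-month calls. On that reading all three come after the exam.

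**Step 4. Could the exam enter the outcome?**
- Against: the study arranges the exam, and its purpose is to decide whether further care is needed. Further care is naturally what comes after it.
- For: no section excludes it. The Addendum calls these visits follow-up physician exams, and they may be hospital visits. They fall between two calls of which Aim 1 says "Contact points at 2 weeks and 1 month correspond with traditional post-injury follow-up visits". The survey asks about care sought separately from care rendered, so a visit without treatment could qualify. Record review has no rule for study exams.

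**Step 5. Illustration, only if exams are counted.** Every input is an assumption:
- p0 = true care-seeking proportion, the same in both phases;
- a = share of otherwise non-seeking intervention patients who attend the exam;
- c = share of those exams recorded as care-seeking.

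Spurious excess = (1 − p0) × a × c.

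| p0 | a | c = 0 | c = 0.1 | c = 0.5 | c = 1 |
|---|---|---|---|---|---|
| 0.30 | 0.25 | 0 | +1.8 | +8.8 | +17.5 |
| 0.30 | 0.50 | 0 | +3.5 | +17.5 | +35.0 |
| 0.50 | 0.50 | 0 | +2.5 | +12.5 | +25.0 |

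Values are percentage points. Example: (1 − 0.30) × 0.50 × 0.5 = 0.175. The table shows how the artefact would scale. It is not an estimate for this trial.

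No figure is given for the attribution issue in Steps 1 to 3, because the documents supply nothing from which to derive one.

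**The case against.** **The wording already excludes the exam.** Patients do not seek an appointment that the study schedules, still less one at home. This is the better reading, and it reduces the second issue to a missing clarification. The aGOSE form is not in the documents and may tell respondents to leave the exam out. The objection does not touch attribution.

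**The pairing is disclosed, and the hypothesis concerns prompt follow-up.** The Addendum does link tool and exams, and the Aim 3 hypothesis can be read for the package. But the Addendum still defines the intervention as the telephone tool, and the regression label and effect-size sentence refer to the tool alone.

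**Aim 3 is exploratory, and attribution is weak anyway.** Both are true. The stepped-wedge rollout meant to control temporal trends was abandoned, which separately limits any causal claim. This lowers the consequence but does not correct the label.

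**Stronger readings that the documents do not support:**
- A reader might infer that the exam is counted, so that the primary outcome is met almost by design. No section says so, and the natural reading is the opposite.
- A reader might infer that the exam must inflate the apparent effect, or that counting exam visits of triage-positive patients gives an upper bound. An exam may prompt care, but it may also reassure patients or replace visits they would have made. The direction is unknown.
- A reader might cite triage question 7, which offers the answer "Sought other care but no further treatment given". It is asked at the 2-week call, before the exam, so it cannot record the exam.

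**Conclusion.** The attribution point holds however the outcome is read: Aim 3 estimates the effect of call plus exam and labels it as triage-tool contact. The size and sign of the exam's share cannot be determined. The conclusion rests on baseline patients having no study exam and on there being no tool-only period, as the documents describe.

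The outcome point holds only as an omission. The exam is probably meant to be excluded, but the plan should say so, because counting hospital exam visits would inflate the intervention proportion. The size of that inflation rests wholly on assumed inputs and is zero if no exam is recorded as care-seeking.

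Severity is minor. Aim 3 is exploratory, the 2-week comparison and Aim 2 are largely unaffected, and the prompt-follow-up hypothesis can still be examined for the package.

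**What to change.** 1. In Aim 3, Data Analysis, name the exposure as triage call plus study physician exam. State that the effect size applies to that package and not to the tool alone.
2. In Aim 3, Outcomes, define the primary outcome in both phases as injury care other than the study exam visit. Use exam records to remove that visit where possible.
3. If the stored data cannot separate exam visits from other care, say so in Section 10 and do not attribute the difference to the tool.

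**Cost.** One exposure label, one outcome sentence and one limitation, with no new data collection. Recruitment and 2-week follow-up have ended, and the documents do not say that the source of each reported visit is stored, so separation may be incomplete. Patients told to return to care may use the exam as that visit. Excluding it may therefore drop some tool-prompted care and bias toward no effect. No tool-only estimate will be available.
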